8.5.1 Review of medical history since last visit

- 8.5.2 Physical examination (vital signs, weight, performance status)
- 8.5.3 Review of changes in concurrent medications
- 8.5.4 Laboratory studies (as defined in Section 8.1.5)
 - a) CBC with differential and platelet count within 2 days prior to treatment
 - b) Serum chemistries (odd # cycles only 5, 7, 9, etc.)
 - c) Serum amylase and lipase (odd # cycles only 5, 7, 9, etc.)
 - d) Serum or urine pregnancy test for WOCBP at Cycle 5 Day 1 and every 12 weeks thereafter
 - e) HIV viral load and CD4/CD8 count at Cycle 5 Day 1 and every 12 weeks thereafter: Viral load studies will be performed using an assay with a limit of detection of 75 copies/ml or less. Repeat Hepatitis B antigen and/or Hepatitis C antibody if positive at baseline.
 - f) Immunologic labs at Cycle 5 Day 1 and every 12 weeks thereafter after consisting of: rheumatoid factor, C-reactive protein, ANA, SPEP, immunoglobulins, and free light chains (FLC).
 - g) Endocrine labs at Cycle 5 Day 1 and every 12 weeks thereafter consisting of: TSH, free T4, TPO, morning ACTH, and morning cortisol if ACTH is abnormal
- 8.5.5 AE assessment
- 8.5.6 Biological sample submissions for correlative studies. Samples will be collected as defined in Section 8.1.10, unless otherwise noted.
 - a) Collect two 6 ml red top tubes for assessment of circulating levels of proinflammatory molecules before cycle 5. Collection, shipping, and storage methods are described in Appendix XV.
 - b) Collect 2x2 mm biopsies in RNALater and formalin before cycle 5 as described in Appendix XIV (optional for KS cases only, with participant consent).
 - c) Collect anal swabs before cycle 5 as described in Appendix XVII (optional for anal cancer cases only, with participant consent).
 - d) Blood draw: Five 8.5mL ACD tubes for assays (HIV DNA, HIV RNA, SCA, and Pheno/ICS) for participants on dose levels 1 (including 240 mg q 2 weeks) or 2 with hematocrit ≥ 25, to be collected pre-dose on Day 1, post-dose on Day 1, and on Day 8 of Cycles 7, 10, 13, 19, 22, 25, 28, 31, 34, 37, 40, 43 and 46 (Appendix XIV). The pre-dose sample and the Day 1 Cycle 1 sample must be drawn on different calendar days and should be collected at least 12 hours apart. The post-dose sample must be drawn between 12 and 36 hours after the infusion has been completed. Every effort should be made to process samples for viable PBMC and plasma on site within 6 hours of collection. The samples will be shipped to the AMC Biorepository via priority overnight service for processing if this cannot occur on site.
 - Five 8.5 mL ACD tubes for assays (HIV DNA, HIV RNA, SCA, and Pheno/ICS) for participants on dose levels -1 or -2 with hematocrit \geq 25, **to be**

collected pre-dose on Day 1, post-dose on Day 1, and on Day 8 of Cycles 7, 13, 19, 25, 31, 37, and 43 (Appendix XIV). The pre-dose sample and the Day 1 Cycle 1 sample must be drawn on different calendar days and should be collected at least 12 hours apart. The post-dose sample must be drawn between 12 and 36 hours after the infusion has been completed. Every effort should be made to process samples for viable PBMC and plasma on site within 6 hours of collection. The samples will be shipped to the AMC Biorepository via priority overnight service for processing if this cannot occur on site.

- e) Blood draw: Twelve 8.5mL ACD tubes for assays (latent reservoir and VOA) for all participants who consent to this optional draw with hematocrit ≥ 25 to be collected **on day 1 of cycle 16.** *These tubes will be shipped directly to the* AMC Biorepository *for processing* (Appendix XVI).
- f) If a participant has not consented to the HIV latent reservoir testing blood draw, two 8.5 yellow top tubes will be collected for herpesvirus load and latent virus studies on day 1 of cycle 16 (Appendix XIV and Appendix XVI).
- 8.5.7 Radiologic assessment of response before cycle 5, and thereafter every 12 weeks. All imaging studies or CT scans should be performed in an identical way to the baseline scan with the same scanner, same scan direction, and consistent arm pointing. Confirmatory scans should also be obtained 4 weeks following initial documentation of objective response. If tumor flare is suspected, the participant must undergo a second scan within a month of the first scan and the case must be discussed with the principal investigator. If progression is documented at that time, participant must come off study. For all cohorts and disease types if a scheduled response assessment is missed, an assessment must be completed and documented prior to drug administration for the next cycle.

For participants with KS, tumor, and response assessment with photographic documentation before odd numbered cycles (5, 7, 9, etc.), as outlined in the KS Tumor Assessment MOP. Response of KS to treatment is described in Section 9.2. Scans will not be required for participants with KS unless clinically indicated.

In participants with HIV-cHL, F-FDG-PET/CT scans will be done at cycles 9 and 13 (weeks 17 and 25). At cycle 24 (week 49), a F-FDG-PET/CT scan will be required for participants who do not have two consecutive negative scans before this time point. A combined FDG-PET/CT or FDG-PET + CT scan with and without IV contrast is required for this study. If a participant has an allergy to IV contrast, a non-IV contrast CT scan will be permitted. If the CT scan of a PET/CT hybrid is performed with both oral and IV contrast with contrast enhancement in the arterial and/or portal venous phase, with at least a 2-slice CT, and is acquired with at least 80 mAs and CT scans are obtained with contiguous sections (with a maximum of 5 mm slice thickness), then the PET/CT scan alone will suffice. If no contrast is used in the FDG-PET/CT, an additional CT scan with contrast is required of the neck, chest, abdomen, and pelvis, see Section 8.1.7.

8.5.8 Dose of nivolumab (or nivolumab and ipilimumab). Prophylactic preinfusion medications should be given if infusion reactions were observed during prior infusions. Vital signs will be monitored pre-infusion and every 30 minutes (+/- 10 minutes) during dosing, and 1-hour post-completion for participants with prior infusion reactions. Participants with no prior infusion reactions may have vital signs monitor pre- and post-infusion only.

8.6 Combination Therapy Solid Tumor Expansion Cohort: Cycle 5-23 Day 1

Unless noted otherwise below, the evaluations may be performed up to three days prior to treatment.

- 8.6.1 Review of medical history since last visit
- 8.6.2 Physical examination (vital signs, weight, performance status)
- 8.6.3 Review of changes in concurrent medications
- 8.6.4 Laboratory studies (as defined in Section 8.1.5)
 - a) CBC with differential and platelet count within 2 days prior to treatment
 - b) Serum chemistries Serum amylase and lipase
 - c) Serum or urine pregnancy test for WOCBP at Cycle 5 Day 1 and every 12 weeks thereafter
 - d) HIV viral load and CD4/CD8 count at Cycle 5 Day 1 and every 12 weeks thereafter: Viral load studies will be performed using an assay with a limit of detection of 75 copies/ml or less. Repeat Hepatitis B antigen and/or Hepatitis C antibody if positive at baseline.
 - e) Immunologic labs at Cycle 5 Day 1 and every 12 weeks thereafter after consisting of: rheumatoid factor, C-reactive protein, ANA, SPEP, immunoglobulins, and FLC.
 - f) Endocrine labs at Cycle 5 Day 1 and every 12 weeks thereafter consisting of: TSH, free T4, TPO, morning ACTH, and morning cortisol if ACTH is abnormal

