4.3.2 Nivolumab and ipilimumab

For Dose Levels 2 and -2 in Stratum 1

1 cycle = 14 days

Nivolumab treatment: A maximum of 46 cycles of nivolumab will be given every 2 weeks

Ipilimumab treatment: A maximum of 16 cycles of ipilimumab given every 6 weeks (on day 1 of every third nivolumab cycle (cycles 1, 4, 7, etc.)) for Dose Level 2, and a maximum of eight cycles of ipilimumab given every 12 weeks, (on day 1 of every sixth nivolumab cycle (cycles 1, 7, 13, etc.)) for Dose Level -2.

Dose Level 2:

- Nivolumab 240 mg q 2 wk x 46 doses
- Ipilimumab 1mg/kg q 6 wk x 16 doses (day 1 of nivolumab cycles 1, 4, 7, 10, 13, 16, 19, 22, 25, 28, 31, 34, 37, 40, 43, and 46)

Dose Level -2:

- Nivolumab 1 mg/kg q 2 wk x 46 doses
- Ipilimumab 1mg/kg q 12 wk x 8 doses (day 1 of nivolumab cycles 1, 7, 13, 19, 25, 31, 37, and 43)

Toxicity management for the combined agents follows the same template guidelines and algorithms that are provided in Appendix X for single agent nivolumab.

Follow the same infusion timing guidelines: nivolumab over 60 minutes and ipilimumab over 90 minutes.

When both nivolumab and ipilimumab are to be administered on the same day, separate infusion bags and filters must be used for each infusion. Nivolumab is to be administered first. The nivolumab infusion must be promptly followed by a saline flush to clear the line of nivolumab before starting the ipilimumab infusion.

Nivolumab cycles may be repeated every 14 days (\pm 2 days). Cycles in which nivolumab and ipilimumab are administered, per the dosing schedule for the assigned dose level 2 or -2, no earlier than 12 days after the last cycle of nivolumab.

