4.3.5 Study procedures by visit and treatment cycle

Note that results of all safety laboratory test (that is, all chemistry and all hematology results) must be obtained and reviewed before ipilimumab administration, as applicable. All laboratory results must be within the established range before ipilimumab is administered. All laboratory samples for the first four cycles of nivolumab must be collected within a window of up to 3 days before administration of nivolumab and/or ipilimumab. Laboratory evaluations using a local laboratory must be performed and the result examined by the investigator before administration of each dose of nivolumab and/or ipilimumab.

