Skin Rash and Oral Lesions	Management/Next Dose for Nivolumab and Combination
Grade 3	$Hold*$ until \leq Grade 1. Resume at same level at investigator discretion.
Grade 4	Off protocol therapy.

^{*}Participants with purpuric or bullous lesions must be evaluated for vasculitis, Steven-Johnson syndrome, TEN, and autoimmune bullous disease including oral lesions of bullous pemphigus/pemphagoid. Pruritus may occur with or without skin rash and should be treated symptomatically if there is no associated liver or GI toxicity. Note skin rash typically occurs early and may be followed by additional events particularly during steroids tapering.

Recommended management: AE management guidelines (Appendix X).

Liver Function (AST, ALT, Bilirubin)	Management/Next Dose for Nivolumab and Combination
≤ Grade 1	Continue protocol therapy.
Grade 2	Hold until UNL or baseline. Resume at same dose level. Consider steroid treatment if > 7 days.
Grade 3	Discontinue protocol therapy if occurring before cycle 5. Initiate IV or PO steroids. May begin nivolumab monotherapy if returns to grade 1 off steroids by week 8 (no earlier than week 6). Hold protocol therapy if occurring after cycle 5. Initiate IV or PO steroids. If not returned to grade 1 off steroids by 6 weeks from missed dose, then off protocol therapy.
Grade 4	Off protocol therapy. Initiate IV steroids.

Continued treatment of active immune-mediated hepatitis may exacerbate ongoing inflammation. Holding drug to evaluate LFT changes, and early treatment are recommended. LFT changes may occur during steroid tapers from other events and may occur together with other GI events including cholecystitis/pancreatitis.

Recommended management: see Hepatic AE management algorithm (Appendix X).

Renal Toxicity	Management/Next Dose for Nivolumab and Combination
≤ Grade 1	No change in dose.
Grade 2	Hold until \leq Grade 1. Resume at same dose level. Steroid treatment if > 7 days.
Grade 3	Hold until ≤ Grade 1. Resume at same dose level.
Grade 4	Off protocol therapy.
Recommended management: see Renal AE management algorithm (Appendix X).	

Diarrhea/Colitis	Management/Next Dose for Nivolumab and Combination
≤ Grade 1	Hold until Grade 0 (if Grade 1) or baseline^. No change in dose.
Grade 2	Hold until Grade 0 or baseline. Steroid treatment if > 7 days

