5.2 Other Guidance

These original ipilimumab guidelines are for investigator information. Treatment management decisions should be based on the information in Section 5.1, treatment algorithms in Appendix X, and further information in the IB.

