Immune-mediated hepatitis and pancreatitis

Hepatic immune-related AEs were mostly clinically silent and manifested as transaminase or bilirubin laboratory abnormalities. Fatal hepatic failure has been reported in clinical trials of ipilimumab. Serum transaminase, bilirubin, and lipase levels must be evaluated before each dose of ipilimumab as early laboratory changes may be indicative of emerging immune-related hepatitis/ pancreatitis and elevations in liver function tests (LFTs) may develop in the absence of clinical symptoms. Increase in LFT or total bilirubin should be evaluated to exclude other causes of hepatic injury, including infections, disease progression, or other medications, and monitored until resolution. Liver biopsies from participants who had immune-related hepatotoxicity showed evidence of acute inflammation (neutrophils, lymphocytes, and macrophages).

Monitor LFTs (hepatic transaminase and bilirubin levels, lipase) and assess participants for signs and symptoms of hepatotoxicity/pancreatitis before each dose of ipilimumab. In participants with hepatotoxicity, rule out infectious or malignant causes and increase frequency of liver function test monitoring until resolution. Withhold ipilimumab in participants with grade 2 hepatotoxicity.

Permanently discontinue ipilimumab in participants with grade 3-5 hepatotoxicity/pancreatitis and administer systemic corticosteroids at a dose of 1 to 2 mg/kg/day of prednisone or equivalent. When LFTs show sustained improvement or return to baseline, initiate corticosteroid tapering and continue to taper over 1 month. Across the clinical development program for ipilimumab, mycophenolate treatment has been administered in participants who have persistent severe hepatitis despite high dose corticosteroids.

Immune-mediated dermatitis

Skin immune-related AEs presented mostly frequently as a rash and/or pruritus. Some participants reported vitiligo associated with ipilimumab administration. Fatal TEN has been reported in clinical trials of ipilimumab.

Monitor participants for signs and symptoms of dermatitis such as rash and pruritus. Unless an alternate etiology has been identified, signs or symptoms of dermatitis should be considered immune-mediated.

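### Up to 7 of the 16 dose-level-2 ipilimumab doses fall on cycles with no scheduled serum chemistry, although Section 4.3.5 requires chemistry before ipilimumab

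*Combined protocol and SAP*

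**What the plan says.** Section 4.3.5 states that "results of all safety laboratory test (that is, all chemistry and all hematology results) must be obtained and reviewed before ipilimumab administration, as applicable". It then adds, without qualification: "All laboratory results must be within the established range before ipilimumab is administered".

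Section 8.5.4(b), for cycles 5 to 46, lists "Serum chemistries (odd # cycles only 5, 7, 9, etc". Item (c) puts the same limit on amylase and lipase. In the main Appendix I grid, the blood count is marked for odd and even cycles, while chemistry and amylase/lipase are marked for odd cycles only.

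Section 4.3.2 gives dose-level-2 ipilimumab on "day 1 of nivolumab cycles 1, 4, 7, 10, 13, 16, 19, 22, 25, 28, 31, 34, 37, 40, 43, and 46".

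Two other places bear on the point. Section 5.2.3 says "Serum transaminase, bilirubin, and lipase levels must be evaluated before each dose of ipilimumab", but Section 5.2 limits its standing: "These original ipilimumab guidelines are for investigator information". Note b of the main calendar requires chemistry, including liver tests, to be reviewed before the nivolumab dose.

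**The concern.** A site cannot follow both the visit schedule and Section 4.3.5 at dose level 2. The schedule says chemistry is for odd cycles only. Section 4.3.5 says ipilimumab may not be given until chemistry has been seen and is in range. The only precedence rule on such matters, in Section 5.1, concerns Section 5.1 against Appendix X and does not reach this conflict.

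What is at stake is a pre-dose safety check. Section 5.1 holds treatment on laboratory values; for grade 2 liver tests the instruction is "Hold until UNL or baseline. Resume at same dose level". A newly raised value cannot trigger that hold at a visit with no liver test. The adverse-event review done at every cycle is not a substitute, because Section 5.2.3 reports: "Hepatic immune-related AEs were mostly clinically silent and manifested as transaminase or bilirubin laboratory abnormalities". Safety is the primary objective of the trial.

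**Working it through.** **Inputs.** Dose-level-2 and dose-level -2 ipilimumab cycles and the ±2-day dosing window: Section 4.3.2. Chemistry through cycle 4: Sections 8.2.4, 8.3.4 and 8.4.4. Chemistry from cycle 5: Section 8.5.4(b). Three-day evaluation window: Section 8.5. Combination expansion cohort: Sections 4.3.4 and 8.6.4 and its own Appendix I grid.

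1. **The plan's own figure.** Every third cycle from 1 to 46 gives (46 − 1)/3 + 1 = 16 doses, which matches the 16 stated.
2. **Doses from cycle 5 on.** Removing cycles 1 and 4 leaves 16 − 2 = 14.
3. **Doses on even cycles.** These are 4, 10, 16, 22, 28, 34, 40 and 46, eight in all. Section 8.4.4 schedules chemistry at cycle 4, so 8 − 1 = 7 have none scheduled: 7 of 16 overall, or 7 of the 14 from cycle 5 on.
4. **Timing.** Cycle c starts in week 2(c − 1) + 1. Cycle 10 is week 19, and the remaining six are weeks 31, 43, 55, 67, 79 and 91.
5. **Shorter treatment.** Over 24 weeks (cycles 1–12) ipilimumab is given at 1, 4, 7 and 10, so 1 of 4 doses is affected. Over 48 weeks (cycles 1–24) there are 8 doses, with 10, 16 and 22 affected, so 3 of 8.
6. **Age of the last scheduled chemistry.** Nominally 14 days. The minimum is 14 − 2 = 12 days, if drawn on the previous dosing day. The maximum is 14 + 2 + 3 = 19 days, or 14 + 2 + 2 = 18 if the two-day limit in note b applies. Dose delays are not counted.
7. **Nivolumab-only even cycles.** Even cycles from 6 to 46 number (46 − 6)/2 + 1 = 21; 21 − 7 = 14 have no ipilimumab at dose level 2.
8. **Other arms.** Dose level -2 gives ipilimumab at cycles 1, 7, 13, 19, 25, 31, 37 and 43, all odd: 0 of 8. In the combination expansion, ipilimumab falls on cycles 1, 4, 7 and 10. Section 8.6.4 has no odd-cycle limit, but that cohort's grid is blank for chemistry on even cycles 6 to 12, so its cycle 10 ipilimumab dose is left unmarked.

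With chemistry scheduled on every ipilimumab cycle, the 7 of 16 falls to 0 of 16.

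**The case against.** The strongest reply is that the rest of the protocol already protects the participant. Note b requires liver tests to be reviewed before nivolumab, and nivolumab is given first on every ipilimumab day. Section 4.2 has blood drawn before each cycle for safety monitoring, and the last sentence of Section 4.3.5 asks for laboratory evaluations before each dose. On this view, a site goes wrong only by ignoring several instructions. These texts do show what was intended. But they contradict an explicit odd-cycles-only rule and a blank grid cell; they do not override them.

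A second reply is that the chemistry sentence in Section 4.3.5 is qualified by applicability, and that no maximum age is set for results after cycle 4. The latest odd-cycle panel might then suffice. The qualifier most naturally means when ipilimumab is due, and the in-range sentence that follows carries no qualifier.

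Several limits stand:

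- A grade 2 value already found on the odd cycle would already trigger a hold. Only an elevation arising after the last panel could be missed.
- Section 5.2.3 says immune-related events commonly start 3 to 10 weeks from first dose; the first affected dose is at week 19. However, Section 5.1 has a specific rule for grade 3 liver toxicity after cycle 5, so late events are foreseen.
- The case for amylase and lipase is weaker. It relies on the general safety-laboratory wording in Section 4.3.5 and note b and on the informational Section 5.2.3. Section 5.1 also continues dosing at asymptomatic grade 2, and at discretion at grade 3.
- Note b speaks of nivolumab. Taken literally, it would extend the conflict to every even cycle. The finding therefore rests on the ipilimumab rules in Section 4.3.5.
- The documents do not show how many participants remain on dose level 2.

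**Conclusion.** The schedule is wrong as written for serum chemistry on dose-level-2 ipilimumab days. Up to 7 of 16 doses per participant have no scheduled chemistry that would allow the Section 4.3.5 check to be made. The figure of 7 assumes all 46 cycles are given; earlier stopping reduces it as shown. For amylase and lipase the same gap exists, but the conflict is indirect and matters less.

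The correction should be made, but it does not threaten the trial's conclusions. The DLT window is 6 weeks and chemistry is scheduled at every visit through cycle 4, so DLT and MTD decisions are untouched. No effect on the toxicity tables has been shown. Dose level -2 ipilimumab is unaffected. In the combination expansion the disagreement is confined to the grid.

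**What to change.** Amend Section 8.5.4(b) and (c) and the main Appendix I grid so that chemistry and amylase/lipase are scheduled on odd cycles and on every cycle in which ipilimumab is given. In the combination expansion grid, mark both rows at cycle 10; full agreement with Section 8.6.4 would also mean marking cycles 6, 8 and 12.

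In the same amendment it would help to state whether four-weekly chemistry is intended on the 14 nivolumab-only even cycles. Note e should also say whether its 48-hour limit applies only to the first infusion, since it refers to Section 8.2, which is Cycle 1 Day 1.

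The cost at dose level 2 is wording plus up to 7 routine panels per participant, at visits that already draw a blood count: at most 7 × 6 = 42 for a six-participant stratum. Section 2.3.9 (April 2019) already reports Stratum 1 dose level 2 as tolerable. If those participants had started by then, 92 weeks of treatment (644 days) would have ended by about January to February 2021, before version 15.0 of 24 August 2023. In practice the dose-level-2 cost would then fall on Stratum 2 only.
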